6.4. Data Handling Convention for Missing Data

Handling of Adverse Event and Injection Site Reaction Severity

If the severity of a TEAE is missing, it will be classified as “severe” in the frequency tables by severity of TEAEs.

Handling of Adverse Event Relatedness

If the assessment of relationship of a TEAE to the study drug or study conduct is missing, it will be classified as “related”.

Handling of Adverse Events or Concomitant Medications with missing or partial start date/time

Imputation of AE and Concomitant Missing and Partial start dates:

Every effort will be made to collect the start dates of all AEs and concomitant medications. However, in the case the start date of an AE or concomitant medication is incomplete or missing, it will be assumed to have occurred on or after the first dose of study medication, except if an incomplete date (e.g., month and year) clearly indicates that the event started prior to treatment. If the partial date indicates the same month or year of the first dose of study medication date, then the start date of the first dose will be imputed, otherwise, the missing day or month by the first day or the first month will be imputed.

Imputation of Partial AE and concomitant Medication Partial end dates:

When only year is present, missing AE/concomitant medication end day and month will be imputed to the earlier of (study end date, 31DECYYYY).

When both month and year are present, missing AE/concomitant medication end date will be imputed to the last day of the month.

There will be no attempt to impute completely missing AE/concomitant medication end dates. Events with an end date missing will be assumed to be ongoing at the time of data cut off.

Missing/Incomplete Medical history dates

Medical history start dates are used to determine the duration of OA at baseline per eCRF data. Completing missing medical history dates will not imputed. Missing month will be imputed to January and missing day will be imputed to the first day of the month.

Handling of Adverse Events classification with missing or partial date/time of first study drug administration

When the date and time of first study drug dose is missing, the date of randomization will be used as the start date for classification of AEs.

When the time of the first study treatment dose is missing, all AEs that occurred on the date of the first study drug dose will be considered as TEAEs.

Handling of missing item data for WOMAC

WOMAC scores will be computed when one pain, one stiffness, or 1-3 physical function items are missing. The missing items will be imputed by the mean of available items within the same subscale. The scores will be set to missing if more items are missing.

Laboratory Safety Variables below lower limit of quantification (LLOQ)

For central laboratory data below the lower limit of quantification, half of the lower limit value (i.e., LLOQ/2) will be used for quantitative analyses.

Missing laboratory, ECG, vital sign, physical exam, neurological exam

No imputations for missing laboratory data, ECG data, vital sign data, physical examination, or neurological examination data will be made.

Handling of Potentially Clinically Significant Abnormalities (PCSA)

If a patient has a missing baseline value they will be grouped in the category “normal/missing at baseline”.

For PCSAs with 2 conditions, one based on a change from baseline value and the other on a threshold value or a normal range, with the first condition being missing, the PCSA will be based only on the second condition.

For a PCSA defined on a threshold and/or a normal range, this PCSA will be derived using this threshold if the normal range is missing; eg, for eosinophils the PCSA is >0.5 GIGA/L or $>ULN$ if $ULN \geq 0.5$ GIGA/L. When ULN is missing, the value 0.5 should be used.

Measurements flagged as invalid by the laboratory will not be summarized or taken into account in the computation of PCSA values.

Date of first/last injection

Date of first injection is the first non-missing start date of dosing filled in the ‘SC Study drug Injection’ CRF module.

If a patient’s date of the last dose is totally missing or unknown, his/her last visit date in the treatment period will be substituted.

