10.6. Additional Statistical Data Handling Conventions

The following analysis and data conventions will be followed:

General rules for handling missing data:

- Rules for handling missing data for efficacy assessments due to missing individual item data will follow each questionnaire's instrument manual.
- If the start date of an AE or concomitant medication is incomplete or missing, it will be assumed to have occurred on or after the intake of study medication, except if an incomplete date (eg, month and year) clearly indicates that the event started prior to treatment. If the partial date indicates the same month or year of the intake of study medication date, then the start date by the study medication intake date will be imputed; otherwise, the missing day or month by the first day or the first month will be imputed.
- No imputations for missing laboratory data, ECG data, vital sign data, or physical examination data will be made.

Visit windows:

• Assessments taken outside of protocol allowable windows will be displayed according to the CRF assessment recorded by the investigator.

Unscheduled assessments:

• Extra assessments (laboratory data or vital signs associated with nonprotocol clinical visits or obtained in the course of investigating or managing AEs) will be included in listings, but not summaries. If more than 1 laboratory value is available for a given visit, the first observation will be used in summaries and all observations will be presented in listings.

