4.6.2. Additional Safety Variables

Additional safety endpoints in this study include:

- Incidence of Adjudicated arthropathy (AA, as confirmed by an independent adjudication committee) through week 36
- Incidence of Destructive arthropathy (DA, as confirmed by an independent adjudication committee) through week 36
- Incidence of treatment-emergent adverse event (TEAEs) through week 16
- Incidence of SNS dysfunction (as diagnosed after consultation with an appropriate specialist, such as a neurologist and/or cardiologist) through week 36
- Incidence of peripheral sensory AEs that require a neurology or other specialty consultation through week 36
- Incidence of all-cause JR surgeries week 36
- Incidence of JRs at telephone survey approximately 52 weeks after last dose of study drug

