5. STATISTICAL METHODS

For continuous variables, descriptive statistics will include the following information: the number of patients reflected in the calculation (n), mean, median, SD, minimum, 1st & 3rd quartiles (Q1 & Q3), and maximum.

For categorical or ordinal data, frequencies and percentages will be displayed for each category.

Period of Observation - Unless otherwise stated, analysis of all safety and non-safety variables captured at multiple visits will be analyzed by the following observation periods:

- The *Pre-Treatment Period* is defined as the time from signing the ICF to before the first dose of study drug.
- The *On-Treatment Period* is defined as the time from the first dose of study drug up to 28 days after the last dose of study drug.
- The *Follow-Up/Post-Treatment Period* is defined from the end of the On-Treatment Period to the date of the follow-up clinic visit (Week 36 visit) or early termination date.

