5.8.2. Adverse Events

All AEs reported in this study will be coded using the currently available version of MedDRA[®]. Coding will be to lowest level terms. The verbatim text, PT, and SOC will be listed.

- *Pre-Treatment Adverse Events* are defined as AEs that developed or worsened during the pre-treatment period.
- *Treatment-Emergent Adverse Events (TEAE)* are defined as AEs that developed or worsened during the On-Treatment Period.
- *Post-Treatment Adverse Events* are defined as AEs that developed or worsened more than 28 days after the last dose of study drug.

Post treatment AEs and all AEs during the study will be summarized similarly as TEAEs.

Summaries of TEAEs by treatment group will include:

- Overview of TEAEs, summarizing number of events, summarizing number and percentage of patients within the specified category
 - Total number of TEAEs
 - Total number of Serious TEAEs
 - Total number of AESIs
 - Patients with any TEAEs
 - Patients with any Serious TEAEs
 - Patients with any AESIs
 - Patients with any TEAEs leading to death
 - Patients with any TEAEs leading to withdrawal from study
 - Patients with any TEAEs leading to permanent study treatment discontinuation
- TEAEs by SOC and PT
 - All TEAEs

- TEAEs by severity: mild, moderate or severe
- TEAEs resulting in permanent study treatment discontinuation
- Treatment-related TEAEs by SOC and PT
 - All treatment-related TEAEs
- TEAEs by PT
 - All TEAEs
 - TEAEs resulting in permanent study treatment discontinuation
- Post-treatment AEs by SOC and PT
 - All post-treatment AEs
 - Post-treatment AEs by severity: mild, moderate or severe
- Serious TEAEs by SOC and PT
- Post-treatment Serious AEs by SOC and PT
- All serious AEs on study by SOC and PT
- Non-serious TEAEs by SOC and PT
- Post-treatment non-serious AEs by SOC and PT
- All non-serious AEs on study by SOC and PT
- All AEs on study by SOC and PT
 - All AEs
 - All AEs by severity: mild, moderate or severe
- Death

Counts will be provided according to treatment group for each PT within each SOC. Percentages will be calculated using the number of patients in each treatment group using the respective SAF.

Primary SOC's will be sorted by decreasing frequency in the fasinumab group. Within each primary SOC, PT's will be sorted by decreasing frequency in the fasinumab group. For tables presenting severity of events, the worst severity will be chosen for patients with multiple instances of the same event.

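### Read literally, the partial start-date rule overrides a known later month and moves follow-up adverse events and medications to the first-dose date

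*SAP*

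**What the plan says.** SAP 6.4 assumes that an adverse event or concomitant medication with an incomplete or missing start date began on or after the first dose, "except if an incomplete date (e.g., month and year) clearly indicates that the event started prior to treatment". The trigger for imputation is: "If the partial date indicates the same month or year of the first dose of study medication date". What follows when the trigger is met, and what follows when it is not, is given next: "then the start date of the first dose will be imputed, otherwise, the missing day or month by the first day". A missing month is filled in the same way, with January. Protocol 10.6 has the same condition: "If the partial date indicates the same month or year of the intake of study medication date". The end-date rule in SAP 6.4 treats year-only dates and month-plus-year dates separately, and it keeps a known month.

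Several classifications rest on the start date:

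- The On-Treatment Period (SAP 5) "is defined as the time from the first dose of study drug up to 28 days after the last dose of study drug".
- Treatment-emergent events (SAP 5.8.2) "are defined as AEs that developed or worsened during the On-Treatment Period".
- Post-treatment events (SAP 5.8.2) "are defined as AEs that developed or worsened more than 28 days after the last dose of study drug".
- A named safety endpoint in SAP 4.6.2 is: "Incidence of treatment-emergent adverse event (TEAEs) through week 16".
- SAP 4.3 uses the start date to separate concomitant from post-treatment medication. SAP 4.4 and 5.4 summarise NSAID-use days and the interval from last dose to first NSAID use.

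SAP 5.3 sends the reader to Section 6.3 for missing medication dates, but 6.3 deals with repeat measurements. The rule is in 6.4.

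**The concern.** The condition joins month and year with *or*. A start recorded as September 2019 shares its year with a March 2019 first dose, so the first-dose date is imputed although the month is known to be September. The fallback to the first day of the known month applies only when neither month nor year matches. The exception protects dates known to be early; nothing protects dates known to be late.

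Two sets of results are exposed. Follow-up adverse events could leave the post-treatment tables and enter the treatment-emergent tables and the week-16 endpoint. Medications begun in follow-up could be shown as on-treatment use from Day 1. For NSAIDs this would inflate the day counts and give a negative interval from last dose to first NSAID use.

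**Working it through.** The plan states no figure here, so there is nothing to reproduce. The check applies the rule as written and a corrected rule to the same dates.

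**Inputs.** The last dose is on Day 85 and week 36 is Day 253 (schedule of events). The On-Treatment Period therefore ends on Day 85 + 28 = Day 113, and follow-up covers Days 114 to 253, which is 140 days.

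**Assumptions.** Dosing is complete and on schedule, only the day of the start date is missing, and calendar dates are illustrative.

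**Rules compared.**
- As written: if the month or the year equals that of the first dose, and the date is not clearly earlier, impute the first-dose date; otherwise impute the first of the month.
- Corrected, for a missing day: impute the first-dose date only if month and year both match; otherwise impute the first of the month.

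**Worked dates, first dose 4 March 2019.**

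| Recorded start | Possible true days | As written | Corrected |
|---|---|---|---|
| April 2019 | 29–58 | Day 1, treatment-emergent | Day 29, treatment-emergent |
| August 2019 | 151–181 | Day 1, treatment-emergent | Day 151, post-treatment |
| September 2019 | 182–211 | Day 1, treatment-emergent | Day 182, post-treatment |
| October 2019 | 212–242 | Day 1, treatment-emergent | Day 212, post-treatment |
| March 2020 | 364–394 | Day 1, treatment-emergent | Day 364, post-treatment |

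The last row lies beyond week 36, where only drug-related serious events are still counted. It shows that matching on month alone also catches the same month a year later.

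**Share reclassified.** For each of 365 first-dose dates, count the days from 114 to 253 whose month and year would be imputed to Day 113 or earlier, and divide by 140. As written, the monthly averages are:

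| First-dose month | Share classed as treatment-emergent |
|---|---|
| January–April | 99–100% |
| May | 84% |
| June | 62% |
| July | 40% |
| August | 18% |
| September–December | 10–11% |

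The average over all first-dose dates is 53%. Under the corrected rule it is 11%, so the excess due to the wording is 53 − 11 = 42 percentage points. The remaining 11% arises because the first of the month can fall on or before Day 113 when the true onset is later in that month.

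**NSAID example, first dose 4 March 2019, use recorded from September 2019 (day missing) to 20 September 2019 (Day 201).**
- Total days: as written, 201 − 1 + 1 = 201; corrected, 201 − 182 + 1 = 20.
- On-treatment days: as written, Days 1 to 113 = 113; corrected, 0.
- Last dose to first NSAID: as written, 1 − 85 = −84 days; corrected, 182 − 85 = +97 days.

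**The case against.** The strongest reply is that the sentence should be read term by term: month when the day is missing, year when the month is missing. The fallback is paired in the same way, the end-date rule keeps a known month, and the literal reading gives results so odd that it was probably not intended. This is plausible as intent, but the text does not say it. The end-date rule separates the two cases explicitly and the start-date rule does not. Even term by term, nothing says that the matching month must be in the same year. A programmer who follows the wording gets the results above.

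Other limits stand in full. SAP 6.4 says that every effort will be made to collect start dates, so the affected records may be few. All adverse events on study are also tabulated, so no event is lost.

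Three stronger inferences are tempting but not supported:

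- *That misdating on Days 30 to 113 inflates the week-16 endpoint.* Many such records would share the first-dose year, but with complete dosing they are treatment-emergent already. Their onset day changes; the count does not.
- *That NSAID use begun after the restriction ended becomes prohibited use in every such case.* The restriction runs at least 16 weeks after the last injection, to about Day 85 + 112 = Day 197. In the example above, Days 182 to 197 fall inside it. What changes there is mainly the period and the duration.
- *That arthropathy models are distorted through an NSAID covariate.* SAP 5.8.9 names no such covariate, and the NSAID summaries are descriptive. The protocol's link between chronic NSAID use and destructive arthropathy comes from another product's data.

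**Conclusion.** The concern holds for the rule as literally written. Among day-missing records with a true onset on Days 114 to 253, about 53% would be classed as treatment-emergent, against about 11% under a corrected rule. This assumes evenly spread first-dose dates and a last dose on Day 85. The absolute number of records is unknown, because the documents give no rate of incomplete dates.

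The damage is misclassification between the on-treatment and follow-up periods, and overstated NSAID exposure. A reader might infer a biased treatment comparison, but the rule is the same in both arms and does not by itself favour either. The nerve-conduction and WOMAC endpoints do not use these dates. Incidence counts through week 36 do not change when an onset moves within that window. The wording should be corrected because it is the pre-specified instruction to the programmer; it does not threaten the main results.

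**What to change.** Replace the imputation sentence in SAP 6.4 and in protocol 10.6 with:

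*If only the day is missing and both month and year equal those of the first dose, or if day and month are missing and the year equals that of the first dose, impute the first-dose date; otherwise impute the first day of the known month (or 1 January if the month is missing). An imputed start date may not be later than a known end date.*

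Correct the cross-reference in SAP 5.3 from Section 6.3 to Section 6.4.

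The cost is one replacement passage in each document and one section number. No new data are needed. The change should be made before unblinding.

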5. STUDY DESIGN

5.1. Study Description and Duration

This is a phase 2, randomized, double-blind, placebo-controlled, multicenter study designed to evaluate the neurological safety of fasinumab compared to placebo in patients with pain due to OA of the hip or knee.

The study duration will be approximately 64 weeks starting at randomization (day 1). The study consists of a screening period of up to 30 days, a 7- to 10-day pre-randomization period (7 days with a +3 day window), a 16-week treatment period (with the last Q4W dose of study drug administered at week 12), a 20-week follow-up period, and a final phone contact approximately 52 weeks after the last dose of study drug is administered (Figure 1).

Figure 1: Study Flow Diagram

EOS- End of study

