5.1.4. Treatment Period

During the treatment period (day 1 through week 16), patients will be permitted to use only study-provided acetaminophen/paracetamol as rescue medication. Patients will record their use of acetaminophen/paracetamol in a diary. Patients should discontinue use of acetaminophen/paracetamol at least 24 hours prior to the start of each study visit in order to minimize the confounding effects of the rescue medication on efficacy measurements.

Neurological, efficacy, and safety assessments will be performed during the treatment period, as outlined in Table 1.

If a patient must undergo JR surgery during the treatment period, he or she will be asked to complete pre-operative imaging and to undergo post-surgery follow-up, as outlined in Table 2.

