7.3.2. Study Drug Discontinuation

Study drug may be temporarily or permanently discontinued due to medical need, as determined by the investigator, medical monitor, or the sponsor and according to the study stopping rules (Section 5.1.7).

Patients who permanently discontinue from study drug will be encouraged to remain in the study and to complete all study assessments. Patients who agree and thus do not withdraw from the study will be asked to return to the clinic for all remaining study visits per Table 1.

Patients who permanently discontinue from study drug and who opt to withdraw from the study will be asked to complete an early termination visit (Section 8.1.3).

Patients who discontinue from study drug prior to study completion due to an AA (see Section 9.6.1.1) should return to the clinic for all remaining study visits per the visit schedule.

In the event that a patient must undergo JR surgery during the treatment or follow-up periods, he/she will be discontinued from study drug and asked to return to the study site for a pre-operative visit and for follow-up safety evaluations 4 and 20 weeks after surgery (as described in Section 8.2.4.7). Pre-operative imaging (X-rays and/or MRI) will be obtained and submitted to the independent adjudication committee for review to exclude or confirm the presence of an AA event. Instructions for the submission process are provided in the study manual.

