8. STUDY SCHEDULE OF EVENTS AND PROCEDURES

8.1. Schedule of Events

Study assessments and procedures are presented by study period and visit in Table 1.

Table 1: Schedule of Events

	Screenii random		Treatment Period							Fol	EOS			
Study Week	Screen	Pre- rand	Baseline	Wk 1	Wk 2	Wk 4	Wk 8	Wk 12	EOT Wk 16	ET¹/ JR Pre- Op	Wk 26	Wk 36	ET ¹ /JR - Pre- Op	Wk 64
Study Day	Up to 30 Days	7 to 10 Days	1	8	15	29	57	85	113		183	253		449
Visit Window (days)				±1	±3	±7	±7	±7	±7		±7	±7		±7
Visit/Phone Contact Number	Visit 1	Visit 2	Visit 3	Visit 4	Visit 5	Visit 6	Visit 7	Visit 8	Visit 9		Visit 10	Visit 11		Phone 1
Screening/Baseline:														
Inclusion/Exclusion ²	X	X	X											
Main study informed consent	X													
Genomics sub-study informed consent ³	X													
Medical history	X													
Medication history	X													
Demographics	X													
Diary instructions		X	X											
Training on pain reporting /patient education brochures ⁴	X	X												
MRI for index joint, contralateral joint & any hip or knee with K-L ≥3	X													
Randomization			X											
Treatment:														
Discontinue non-study pain medications		X												
Study drug SC injection ⁵			X			X	X	X						
Dispense to home paracetamol/acetaminophen		X	X			X	X	X						
Paracetamol/ acetaminophen accountability			X		X	X	X	X	X	X				
Record rescue medication use in diary ⁶		X	X	X	X	X	X	X	X	X				
Concomitant therapies	X	X	X	X	X	X	X	X	X	X	X	X	X	
Patient-Completed Assess	sments/Effic	acy:												
WOMAC ^{7, 22}	X ⁷		X		X	X	X	X	X	X	X	X	X	

Regeneron Pharmaceuticals, Inc.

Page 42 of 83

	Screenii random	ization	Treatment Period						Fol	EOS				
Study Week	Screen	Pre- rand	Baseline	Wk 1	Wk 2	Wk 4	Wk 8	Wk 12	EOT Wk 16	ET ¹ /	Wk 26	Wk 36	ET ¹	Wk 64
Study Day	Up to 30 Days	7 to 10 Days	1	8	15	29	57	85	113	JR Pre-	183	253	/JR Pre-	449
Visit Window (days)				±1	±3	±7	±7	±7	±7	Op	±7	±7	Op	±7
Visit/Phone Contact Number	Visit 1	Visit 2	Visit 3	Visit 4	Visit 5	Visit 6	Visit 7	Visit 8	Visit 9	Ор	Visit 10	Visit 11	Оþ	Phone 1
Neurological Assessments:														
Nerve conduction	X8						X		X	X^9		X	X^9	
Neurological examination (full)	X		X		X	X	X	X	X	X	X	X	X	
Survey of autonomic symptoms ²²	X		X		X	X	X	X	X	X	X	X	X	
Orthostatic blood pressure assessment and heart rate ^{10,11}	X	X	Х		X	X	X	X	X	X	X	X	X	
Safety:														
Vital signs ¹¹	X		X		X	X	X	X	X	X	X	X	X	
Electrocardiogram	X								X	X				
Physical examination and weight	X								X	X		X	X	

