5.6.2. Treatment Exposure

The treatment exposure to fasinumab and placebo SC doses will be calculated as:

- (Date of last administration of study drug - date of the first study drug administration after randomization) + 28

The duration of exposure will be summarized for each treatment group by descriptive statistics.

The number and percentage of patients randomized and exposed to double-blind study drug will be presented by specific time periods for each treatment group. The time periods of interest are specified as: ≥ 1 day, ≥ 29 days, ≥ 57 days, ≥ 85 days and ≥ 113 days.

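### SAP 6.4 fills a wholly missing last-dose date with the last treatment-period visit, often the non-dosing week-16 visit, which overstates exposure and on-treatment time for the few patients affected (minor).

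*SAP*

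**What the plan says.** **The rule.** SAP 6.4, under the heading on first and last injection dates, covers a last-dose date that is missing altogether or unknown: "his/her last visit date in the treatment period will be substituted". It does not require that visit to be one at which drug was given. In the same place, the first-injection date is taken from the injection module of the case report form.

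**The schedule.** Protocol 5.1 describes a 16-week treatment period "with the last Q4W dose of study drug administered at week 12". Protocol 5.1.4 runs that period from day 1 through week 16. In Table 1 of the protocol and of the SAP, the row "Study drug SC injection" is marked at baseline and weeks 4, 8 and 12, and not at week 16 (Day 113).

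**Patients who stop early.** Protocol 7.3.2: "Patients who permanently discontinue from study drug will be encouraged to remain in the study and to complete all study assessments".

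**What depends on the date.** SAP 5.6.2 calculates exposure as last dose minus first dose plus 28 days. The On-Treatment Period in SAP 5 "is defined as the time from the first dose of study drug up to 28 days after the last dose of study drug". SAP 5.8.2 uses that period to separate treatment-emergent from post-treatment adverse events. SAP 5.8.4 and 5.8.5 use it for laboratory and vital-sign summaries, and SAP 5.8.9 uses it to split joint replacements by period. SAP 5.4 also summarises the days from last dose to first NSAID.

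**The concern.** The substitute date should be one on which the patient could have been dosed. Under the calendar definition of the treatment period, its final visit is week 16, when no injection is scheduled. The rule reaches that date for anyone who attends week 16, whether all four doses were given or dosing stopped at week 4. No other part of the SAP caps or overrides it.

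Three things are at stake for an affected patient. Exposure is credited that no injection supports. Adverse events after the true on-treatment window move into the treatment-emergent tables. The gap between last dose and first NSAID is shortened or becomes negative, although Protocol 7.7.1 restricts NSAIDs until at least 16 weeks after the last injection. The error is largest in patients who stopped drug early and stayed in the study.

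**Working it through.** **Inputs.** Target days from Table 1: doses on Days 1, 29, 57 and 85; week-16 visit on Day 113; windows of ±7 days at weeks 12 and 16. First dose is taken as Day 1.

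**Formulas.** Exposure = (last dose day − first dose day) + 28 (SAP 5.6.2). End of on-treatment period = last dose day + 28 (SAP 5).

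**Reproducing the plan.** Four doses on schedule: (85 − 1) + 28 = 112 days = 16 weeks, with the on-treatment period ending on Day 85 + 28 = 113. This matches the stated 16-week treatment period.

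**Under the substitution.** With Day 113 as the last-dose day: (113 − 1) + 28 = 140 days = 20 weeks, ending on Day 113 + 28 = 141.

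| True last dose | True exposure | True end | Exposure under rule | Excess | AE onset days relabelled |
|---|---|---|---|---|---|
| Week 12 (Day 85) | 112 days | Day 113 | 140 days | 28 days | 114–141 |
| Week 8 (Day 57) | 84 days | Day 85 | 140 days | 56 days | 86–141 |
| Week 4 (Day 29) | 56 days | Day 57 | 140 days | 84 days | 58–141 |
| Day 1 only | 28 days | Day 29 | 140 days | 112 days | 30–141 |

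**Visit windows.** A week-12 dose on Days 78 to 92 followed by a week-16 visit on Days 106 to 120 gives an excess between 106 − 92 = 14 and 120 − 78 = 42 days.

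**Exposure categories.** The top category in SAP 5.6.2 is 113 days or more. A patient with four doses exactly on schedule has 112 days and does not reach it. A patient given 140 days by substitution does, even after a single injection.

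**NSAID interval, illustrative days.** Last dose on Day 29 and first NSAID on Day 100: the true interval is 100 − 29 = 71 days. The rule gives 100 − 113 = −13 days.

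**Effect on group summaries, assuming one affected patient in a group of 90.** Mean exposure rises by 28/90 = 0.3 day (week 12) or 84/90 = 0.9 day (week 4). An exposure category changes by 1/90 = 1.1 percentage points.

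**The case against.** **The trigger is rare.** This stands. The date must be missing altogether. Injections are given in clinic as the last procedure of a dosing visit, followed by about an hour of observation (Protocol 7.1 and Table 1 footnote 5). Dates go into a dedicated form module, and accountability records must also hold them (Protocol 7.6.3). The documents give no expected number of affected patients.

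**Main results are not touched.** This also stands. A reader might infer that the rule threatens the primary safety result. It does not: SAP 5.8.1 includes nerve-conduction data collected after stopping treatment, up to week 16. The arthropathy, sympathetic dysfunction, peripheral sensory and joint-replacement incidence endpoints run through week 36 regardless of the last dose, and the time-to-event measures start from the first dose. No adverse event is lost, because post-treatment and all on-study events are tabulated as well; an event only changes label. For a patient dosed through week 12, the longer window adds almost no scheduled laboratory or vital-sign data: after week 16 (Day 120 at the latest), the next visit is week 26 (Day 176 at the earliest).

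**The direction is cautious.** This stands in part. SAP 6.4 resolves other gaps towards attribution, for example treating missing severity as severe and missing relatedness as related. A wider treatment-emergent window fits that policy. Overstated exposure and a distorted NSAID interval do not.

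**Circularity.** A reader might infer that the rule is circular, since the On-Treatment Period needs the very date that is missing. The documents do not support stating this alongside the figures above. SAP 6.4 says treatment period, which SAP 2.1 and Protocol 5.1.4 define by calendar, and that reading is not circular. Protocol 10.4.4 does use the term in a dose-based sense, but under that sense the Day 113 figures would not follow.

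**Conclusion.** The point holds, at minor severity. As written, the rule gives a last-dose date on which no injection is scheduled, for completers and for patients who stop drug but attend week 16. Each such patient gains 28 days of exposure and on-treatment time if the true last dose was at week 12, and up to 112 days if only the first dose was given.

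This rests on the calendar definition of the treatment period and on visits at their target days. There is no excess when the last treatment-period visit was itself the last dosing visit. Patients who withdraw early take an earlier visit date, so their excess is smaller or nil. The consequences are confined to exposure, the labelling of events and measurements by period, and the NSAID interval, probably in few or no patients.

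**What to change.** Replace the sentence in SAP 6.4 with:

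> If the last-dose date is wholly missing or unknown, the date of the last visit at which an injection is recorded as given (injection CRF module or drug accountability records) will be substituted; if none is recorded, the last attended scheduled dosing visit (Day 1, week 4, 8 or 12) at which study drug was not documented as withheld or missed and, for patients who discontinued treatment, on or before the discontinuation date.

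The condition on withheld or missed doses is needed because a patient can attend a dosing visit and receive nothing (Protocol 7.1 and 7.3.2.2). The discontinuation-date limit applies only to patients who have such a date, so completers are covered too. The cost is one SAP sentence and a small change to the derivation, with no new data.
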